3.9.8 Safety follow up visit (Visit 8; Day 84+14)

The purpose of this visit will be to ensure lack of any delayed adverse events. These procedures can be combined with visit 7 for early termination subjects who request withdrawal from treatment.

- Concomitant medications
- Adverse events
- Vital signs, weight, height, and orthostatics
- Physical Examination
- Neurological Examination
- Urological Examination
- Urinalysis
- UPDRS
- PVR
- PPBC
- Serum pregnancy test (SPT) for WOCP

The urologic examination, PVR, and urinalysis may be obtained at a separate visit, within the 3 days preceding scheduled Visit 8.

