During the 2-week run-in placebo period all subjects will receive placebo tablets matching the 25 mg mirabegron extended release tablets. During the first two weeks of the double-blind placebo-controlled phase, subjects will be randomized to either 25 mg extended release mirabegron or matching placebo (2:1 ratio). During the following 10 weeks of the double-blind placebo-controlled phase, subjects tolerating treatment without side-effects will be escalated to 50 mg mirabegron (two 25 mg mirabegron extended release tablets) or matching placebo (two placebo tablets); subjects experiencing side-effects that do not preclude continuation of the study will continue at the dosage level of one 25 mg extended release mirabegron tablet or matching placebo daily. Subjects who have escalated to 50 mg mirabegron or matching placebo and experience side-effects at that level, will be allowed one dose reduction to 25 mg mirabegron or matching placebo.

Depending on dose level, one or two tablets will be administered daily, with or without food, swallowed whole with water; chewing, crushing or dividing is not allowed.

Primary Endpoint:

Relative mean change to the MoCA score between randomization visit (Visit 3) and week 14 visit (Visit 7).

Table 1. Schedule of Activities:

VISIT/PROCEDURE:	Screening Visit	Baseline Visit	Randomizati on	Low dose phase	Dose escalation	High dose phase	End of TX / Early Term	Follow-up / Week 16
	V 151t					•		
Visit number	1	2	3	4 phone	5	6	7	8
Visit time	week -4 to -6	week -2	day 0	day 7	day 14	day 42	day 84	day 98
Informed consent	X							
Inclusion/Exclusion criteria	X							
Past history/demographic	X							
Neurological and physical exam	X	X			X		X	X
Urologic exam	X *				X*			X*
Cystoscopy	X*							
Concomitant medication	X	X	X	X	X	X	X	X
Adverse events		X	X	X	X	X	X	X
Study drug compliance			X	X	X	X	X	
UPDRS	X				X		X	X
Vital signs (includes weight, height and orthostatics)	X	X	X		X		X	X
ECG	X				X		X	
Pregnancy test (for WOCP)	X							X
Urinalysis	X*				X*		X	X*
Blood samples (safety)	X						X	
OABQ	X		X		X	X	X	
3-day VD training and concordance	X							
3-day VD assessment		X	X		X	X	X	
PVR	X*				X*			X*
PPBC		X	X		X	X	X	X
CQ			X				X	
UPDRS-6			X				X	
MoCA	X		X				X	
Map Search			X				X	
HVLT			X				X	
TMT A and B			X				X	
BAI			X				X	
BDI-II			X				X	
ESS			X				X	
PFS			X				X	
PIMS			X				X	
Drug dispense		X	X			X		

^{*} Procedures performed during the urology visit

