3.9.5 Dose escalation visit (Visit 5; Day 14)

The purpose of this visit is to assess adverse events, medication compliance, and obtain interim measures for analyses.

- Concomitant medications
- Adverse events
- Study drug compliance
- Vital signs, weight, height, and orthostatics
- Physical Examination
- Neurological Examination
- ECG
- UPDRS
- Urologic examination
- PVR
- Urinalysis
- OABQ
- 3-day VD assessment
- PPBC
- Study drug dose escalation instructions

The urologic examination, PVR, and urinalysis may be obtained at a separate visit, within the 3 days preceding scheduled Visit 5. At the conclusion of Visit 5, subjects will be instructed to increase the dose to ge2 mirabegron 25 mg extended release - matching placebo tablets daily (placebo arm) or 2 mirabegron 25 mg extended release tablets daily (active treatment arm). Thus all subjects will begin receiving 2 identical looking tablets daily.

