3.9.6 High-dose phase maintenance visit (Visit 6; Day 42)

The purpose of this visit is to establish interim overall tolerability of the medication, medication compliance, and obtain interim measures for analysis.

- Concomitant medications
- Adverse events
- Study drug compliance
- OABQ
- 3-day VD assessment
- PPBC
- Study drug dispense

At the conclusion of Visit 6, subjects will be dispensed mirabegron 25 mg tablets or matching placebo. Study drug will be administered in the form of 2 mirabegron 25 mg, matching placebo tablets daily (placebo arm) or 2 mirabegron 25 mg tablets daily (active treatment arm). Thus all subjects will continue to receive 2 identical looking tablets daily. Sufficient study drug will be dispensed to last until the end of treatment visit (Visit 7).

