3.9.7 End of treatment / Early termination visit (Visit 7; Day 84)

During Visit 7, screening and baseline safety and tolerability as well as efficacy and outcome measures will be repeated.

- Concomitant medications
- Adverse events
- Study drug compliance
- Vital signs, weight, height, and orthostatics
- Physical Examination
- Neurological Examination
- ECG
- UPDRS
- Blood samples for chemistry and hematology (Na, K, Cl, HCO₃, blood glucose, BUN, creatinine, GFR, AST, ALT, total bilirubin, Alkaline phosphatase, GGT, CBC with differential and platelets)
- Urinalysis
- OABO
- 3-day VD assessment
- PPBC
- CQ

- UPDRS-6
- MoCA
- Map Search
- Hopkins Verbal Learning Test (HVLT)
- Trail Making Test (TMT) parts A and B
- Beck Anxiety Inventory (BAI)
- Beck Depression Inventory version II (BDI-II)
- Epworth Sleepiness Scale (ESS)
- Parkinson Fatigue Scale (PFS)
- Parkinson's Impact Scale (PIMS)

If a subject at any point during the study requests to withdraw from treatment, they should return for an early termination visit. The procedures of visit 7 and visit 8 can be combined in a single visit for early termination subjects. It would be desirable that subjects continue to receive study drug until early termination procedures can be completed.

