3.11.4 Post-void Residual (PVR)

The post-void residual (PVR) urine test measures the amount of urine left in the bladder after urination. The test is used to help evaluate incontinence in women and men, problems with urination, and benign prostatic hyperplasia. The amount of leftover (residual) urine will be measured using cystoscopy or ultrasound.

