6.1.8 Dose increase / Dose reduction

One scheduled dose increase will occur for the active treatment group subjects as described above at visit 5. Dose de-escalations will not be allowed prior to dose escalation (visit 5). If the subject is not tolerating study drug prior to dose escalation then the Principal Investigator will consider their withdrawal from the study. One dose de-escalation will be allowed after the dose escalation has taken place (visit 5). Thus, subjects in both treatment groups will be allowed to reduce their daily dose to 1 tablet daily, at the discretion of the Investigator. No re-escalations will be allowed due to the short duration of the study. If subjects cannot tolerate 1 tablet a day, then the Principal Investigator will consider withdrawal of the subject from the study.

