7.3 Analysis population

The analysis population is based on intent-to-treat and will consist of all participants who received at least one dose during the double-blind placebo-controlled phase. Participants who withdraw from the study or are withdrawn by the study PI will be described by screening/baseline characteristics, but excluded from analyses.

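### For completers who escalate, the only scheduled blood pressure on two tablets falls on Day 84, when treatment ends; adding vital signs at Visit 6 (Day 42) is a cheap, minor safety improvement

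*Combined protocol and SAP*

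**What the plan says.** Section 3.9.5 places vital signs, PVR and the urologic examination at Visit 5 and then states: "At the conclusion of Visit 5, subjects will be instructed to increase the dose". The urology part may be done up to three days earlier. Everything measured at Visit 5 is therefore on one tablet.

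Section 3.9.6 says of Visit 6: "The purpose of this visit is to establish interim overall tolerability of the medication". Its list has concomitant medications, adverse events, compliance, bladder questionnaires, the diary and drug dispensing. It has no vital signs.

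Section 3.9.7 opens: "During Visit 7, screening and baseline safety and tolerability as well as efficacy and outcome measures will be repeated". The list that follows includes vital signs with orthostatics, an ECG and urinalysis, but neither PVR nor the urologic examination. Those return at Visit 8, where section 3.9.8 adds: "The urologic examination, PVR, and urinalysis may be obtained at a separate visit, within the 3 days preceding scheduled Visit 8". Table 4 shows no study drug between Visits 7 and 8. Table 1 agrees with the visit lists throughout.

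Section 6.1.8 allows one step down to one tablet after escalation, at the investigator's discretion. Section 1.3.1 presents that step as the counterpart to shortening the titration to two weeks.

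**The concern.** The label in Appendix I (section 5.1) says that the drug can raise blood pressure and recommends periodic readings. A rise is found mainly by measuring it, and asking about adverse events can miss it. The plan's safeguard on the target dose is the one permitted dose reduction, but no scheduled blood pressure on two tablets exists while that reduction can still be used. Visit 6 is the natural place for one: it is in person, it dispenses the second supply of drug, and its stated purpose is tolerability.

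A related gap affects reporting more than dosing. The label mentions post-marketing urinary retention, and the plan lists PVR among its safety assessments (section 3.11.4). Yet no completer has a scheduled PVR on two tablets, so the final report could not describe PVR on the target dose from scheduled data in completers.

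**Working it through.** **Step 1: count the scheduled readings.** Sources are Table 1, sections 3.9.1 to 3.9.8 and Table 4, for a completer who escalates and is not reduced.

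| Visit | Day | Tablets at that time | Vital signs | PVR and urologic exam |
|---|---|---|---|---|
| 1 | screening | none | yes | yes |
| 2 | -14 | none | yes | no |
| 3 | 0 | one (run-in placebo) | yes | no |
| 4 (phone) | 7 | one | no | no |
| 5 | 14 (urology 11 to 14) | one | yes | yes |
| 6 | 42 | two | **no** | no |
| 7 | 84 | two | yes | **no** |
| 8 | 98 (urology 95 to 98) | none | yes | yes |

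The two-tablet phase lasts 84 - 14 = 70 days, or 70/84 = 83% of the double-blind period. Scheduled blood pressures in it: one, at Day 84. Scheduled PVRs: none. A subject reduced to one tablet before Day 84 has no scheduled blood pressure on two tablets at all.

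**Step 2: what a Visit 6 reading would add.** Day 42 is 42 - 14 = 28 days after escalation, and the label gives steady state within 7 days of once-daily dosing. It leaves 84 - 42 = 42 treatment days in which a reduction could matter. The Day 84 reading leaves none.

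**Step 3: expected yield.** Inputs are the label's section 12.2 rates for placebo, 25 mg and 50 mg. A systolic rise of at least 15 mmHg occurred in 5.3%, 5.1% and 6.7%. A diastolic rise of at least 10 mmHg occurred in 4.6%, 4.1% and 6.6%. The label gives no denominators for these, so I assume those of its adverse event table (1380, 432, 1375).

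- Systolic, 50 mg against placebo: 6.7 - 5.3 = 1.4 points. SE = sqrt(0.067 × 0.933/1375 + 0.053 × 0.947/1380) = 0.90 points, so the 95% CI is -0.4 to 3.2. In 20 active subjects: 20 × 0.014 = 0.28.
- Diastolic, 50 mg against placebo: 6.6 - 4.6 = 2.0 points. SE = sqrt(0.066 × 0.934/1375 + 0.046 × 0.954/1380) = 0.88 points, so the 95% CI is 0.3 to 3.7. In 20 subjects: 20 × 0.020 = 0.40.
- At 25 mg the same calculation gives -0.2 (-2.6 to 2.2) and -0.5 (-2.7 to 1.7).
- Sensitivity: the micturition denominators in label Table 3 are 473 + 425 + 426 = 1324 on 50 mg and 480 + 433 + 415 = 1328 on placebo. They give -0.4 to 3.2 and 0.25 to 3.75, so the choice hardly matters.

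Other label figures are more reassuring. Hypertension adverse events were 7.5% at 50 mg against 7.6% on placebo (11.3% at 25 mg). The mean rise over placebo in OAB patients was about 0.5 to 1 mmHg.

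**Step 4: how often a 15/10 mmHg trigger would fire.** At the 50 mg rates, 20 × 0.067 = 1.34 active subjects would meet the systolic rule and 20 × 0.066 = 1.32 the diastolic rule. That is between 1.34 (full overlap) and 2.66 (no overlap) of 20. Most of this is background: 5.3/6.7 = 79% and 4.6/6.6 = 70% of the rates are also seen on placebo. That is why the trigger should lead to a repeat reading before any dosing decision. The documents give no basis for the yield of an absolute 180/110 mm Hg limit.

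**Step 5: PVR at Visit 8.** Urology at Day 95 to 98 is 11 to 14 days, or 264 to 336 hours, after the last dose. With the label's half-life of about 50 hours, that is 264/50 = 5.3 to 336/50 = 6.7 half-lives, leaving 0.5^5.28 = 2.6% to 0.5^6.72 = 0.9% of the drug. It is an off-drug measurement.

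**The case against.** The strongest reply is that monitoring is already adequate. Blood pressure is taken supine and standing at six visits, including once on two tablets. The label asks for periodic readings and sets no interval. Adverse events are collected at Visit 6, unscheduled visits can add readings, Visit 7 has a complete physical examination, and an external committee reviews safety. The label data show little or no effect at 50 mg. All of this stands, and it limits the point to a minor one. It does not supply a scheduled reading on the target dose in time to use the dose reduction.

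A reader might infer that PVR must move from Visit 8 to Visit 7. The documents do not support that as a required change. Section 3.9.8 gives Visit 8 the purpose of looking for delayed events, so an off-drug urology check there is a reasonable choice, and moving it would give that check up. A PVR at Day 81 to 84 cannot prompt a dose change and still leaves 81 - 14 = 67 days on two tablets without one. A urology visit in those three days could also overlap the Visit 7 diary, which feeds secondary efficacy measures. If no case were seen in 20 subjects, only rates above 1 - 0.05^(1/20) = 13.9% would be excluded. Existing cover includes screening urology with cystoscopy, an on-drug PVR at Visit 5, the exclusion of OAB antimuscarinics, and the diary's volume per void at Visits 6 and 7. The label also reports a controlled safety study in bladder outlet obstruction without increased retention, though it still advises caution when obstruction is clinically significant.

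A reader might also take the opening sentence of section 3.9.7 as a promise of PVR at Visit 7. It is a general lead-in. The itemised list and Table 1 agree with each other, and cystoscopy is likewise not repeated.

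**Conclusion.** The point holds as a minor gap in scheduled safety measurement. For completers who escalate, there is one scheduled blood pressure on two tablets, at Day 84, and none that can inform the dose reduction. Adding one at Visit 6 is worthwhile because it costs almost nothing. The expected benefit is small, about 0.3 to 0.4 excess threshold events in 20 active subjects. The systolic interval includes zero.

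That size rests on two assumptions: the borrowed denominators, and the transfer of label rates to this trial. The label populations had a mean age of 59 and were not selected for Parkinson disease. Section 1.3 calls sympathetic dysfunction very common in Parkinson disease, so the true figure could differ in either direction.

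On PVR, the supported conclusion concerns reporting: scheduled on-drug PVR in completers describes one tablet only. Early-termination subjects may combine the Visit 7 and 8 procedures and so could have a PVR on two tablets, but section 7.3 says: "Participants who withdraw from the study or are withdrawn by the study PI will be described by screening/baseline characteristics, but excluded from analyses". Section 7.4.4 does not say whether that rule extends to safety summaries.

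A reader might infer that the trial leaves the target dose unmonitored, or that its main result is at risk. Neither follows. Visit 7 measures blood pressure on two tablets, adverse events are collected throughout, and the primary endpoint, the change in MoCA from Visit 3 to Visit 7, is untouched.

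**What to change.** Add vital signs with supine and standing blood pressure to Visit 6, in Table 1 and section 3.9.6. State that a repeat reading and investigator review follow if supine systolic pressure is at least 180 or diastolic at least 110 mm Hg (the entry limit in section 3.4 and label section 5.1). The same should follow if the rise from Visit 3 is at least 15 mm Hg systolic or 10 mm Hg diastolic (the label's reporting thresholds). Including the rise criterion matters because a 15/10 mm Hg rise need not reach 180/110. The cost is a few more minutes at an existing in-person visit and a small number of repeat readings, many of them in subjects whose rise is not due to the drug. No planned analysis changes.

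For PVR, keep the schedule and add a sentence to section 7.4.4: conclusions about on-drug PVR in completers apply to the one-tablet dose, Visit 8 values are off drug, and early-termination values are listed separately with the dose at the time. Moving PVR to Visit 7 remains the sponsor's option. If that is done, the PVR result that prompts a Visit 8 repeat should be defined, and the urology visit kept off the diary days.

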3.9.9 Unscheduled visit

Unscheduled visits can be conducted at the Investigator's discretion. Procedures during these visits will be focused to the problem that precipitated the visit. If a subject develops intolerable side effects during the treatment period, but wishes to continue in the study, he/she may come in for an unscheduled visit. A dose reduction is permitted only once during treatment and only after the dose escalation to mirabegron daily dose of 50 mg vs. placebo. The dose can be decreased at that time to 25 mg of mirabegron vs. placebo. Subjects that require such dose reduction will be receiving one tablet daily. Further dose reductions will not be permitted, and, if deemed necessary, subjects will be brought in for early termination.

Changes in the antiparkinsonian agents or cognitive enhancers will only be permitted to a limited degree, and only if, in the opinion of the investigator, are not likely to alter the outcome measures of the study. Naturally, if these medication changes are triggered by worsening of the PD or cognitive symptoms, such worsening will have to be logged as an adverse event or serious adverse event as appropriate.

3.10 Efficacy Assessments

3.10.1 Procedures related to primary end point (cognitive tolerability)

3.10.1.1 Montreal Cognitive Assessment (Appendix II)

The Montreal Cognitive Assessment (MoCA)²³ is a brief cognitive battery, designed initially as a screening instrument for mild cognitive dysfunction. It has been standardized for use in Parkinson disease²⁴, and normative data have been developed with proposed cut-offs for both mild cognitive impairment and dementia.²⁶ It is generally sensitive to mild cognitive difficulties common in PD even in the absence of dementia. It assesses the following cognitive domains: attention and concentration, executive function, memory, language, visuoconstructional skills, conceptual thinking, calculations, and orientation. Three versions are available to improve test-retest reliability and reduce practice effect. Time to administer the MoCA is approximately 10 minutes. The total possible score is 30 points; a score of 26 or above is considered normal. A one-point correction is added for education of less than 13 years.

3.10.1.2 Map Search

Map Search is a test of selective attention, developed as one of the components of Tests for Everyday Attention (TEA).²⁹ It is a 2-minute, timed task that involves searching a map for a target symbol among competing and irrelevant distracters. Subjects are

instructed to circle as many of the target symbols as possible. By the use of different colored pens the number of target symbols circled in 1 minute versus the total for 2 minutes can be counted. There are 80 of each type of symbol.

3.10.1.3 Hopkins Verbal Learning Test (HVLT)

The HVLT is a validated test of episodic verbal memory. ³⁰ The revised HVLT-R will be utilized for this study. ³¹ It consists of a 12-item word list derived from three semantic categories, 4 words for each category. Categories are generally simple, straightforward and of common usage, e.g. 'precious stones', 'animals', etc. One of five available forms will be randomly administered to each subject as per the standard instructions. The list is read to the subject on three consecutive learning trials. After each trial, subjects are asked to recall the words. A delayed recall trial follows 20–25 minutes after the third learning trial. Finally, subjects are presented with a 24-word list composed from the 12 original words together with 12 novel, distractor words, and are asked to respond with 'yes' or 'no' to the question of which words were part of the original list. The following scores will be calculated: (a) sum of words correctly recalled on the three learning trials, (b) number of words recalled on the delayed recall trial, and (c) recognition discrimination index (true positive minus false positive responses).

3.10.1.4 Trail Making Test (parts A and B)

The Trail Making Test (TMT) is a measure of attention, speed and mental flexibility.³² It requires the subject to connect, by making pencil lines, 25 encircled numbers randomly arranged on a page in proper order (Part A) and 25 encircled numbers and letters in alternating order (Part B). Subjects are presented with one example prior to the administration of each part. Mistakes are counted and the subject is told when they have made a mistake by the examiner, and are directed to correct the mistake. The time to complete each part in seconds is the main measure obtained from this test. No penalty is given for mistakes.

3.10.2 Procedures related to secondary end points

3.10.2.1 Overactive Bladder Questionnaire (OABQ – Appendix III)

Overactive bladder (OAB) is characterized by symptoms of urinary frequency and urgency, with and without incontinence. The Overactive Bladder Questionnaire³³ (OABQ) is a 33-item, self-administered instrument that contains a symptom bother scale (8 items to be administered during visits 1, 3, 5, 6, and 7) and a health-related quality of life scale (HRQL-to be administered during visits 3 and 7), pertaining to OAB symptoms

impact on HRQL. The OABQ was developed from an initial version of 62 items to its final form and has been shown to be a valid and reliable instrument in distinguishing normal from clinically diagnosed continent and incontinent patients. In addition to measuring the severity of symptom bother, the OABQ is also useful in quantifying the negative impact of both continent and incontinent symptoms on HRQL. This instrument has been used as an efficacy outcome in the pivotal randomized clinical trials of mirabegron, and the drug's efficacy was indeed accurately reflected in the instrument. The OABQ has also been studied and found useful in PD. ³⁴

3.10.2.2 3-Day Voiding Diary (Appendix IV)

A 3-day voiding diary will be implemented to collect additional efficacy measures of average daily incontinence episodes, micturition frequency, and volume voided per micturition. Subjects will be trained in the diary completion. A toilet hat will be supplied for volume measurement. Subjects are instructed to record the times of every voiding event during three consecutive days; amount voided with each event; instances of leaking including incontinence; whether there was associated urge to void with any voiding event; and, whether they had to get out of bed to void.

